6.2 Scheduled Visits and Phone Calls

The scheduled visits are summarized in Table I and include the initial face to face visit along with face to face visits at day 30, 60, and 90. There will also be weekly phone calls to the patient. No monthly visits will occur if the subject has stopped wear. The phone calls will be conducted within no more than 2 days before or after the scheduled date. The scheduled visits will be conducted within no more than 5 days before or after the scheduled date. During subject wear, phone calls will be accompanied by the weekly data review. The data review will need be completed before the phone call. There will be a weekly report sent to the site.

During the optional extended 90 day wear period, scheduled clinic visits and weekly phone calls will continue to take place following the procedures in Visits 2-4 with the exception of 6.2.4.6 (asking again for additional wear). Chart review, study questionnaires, and a follow up phone call will take place at 6 months and 1 year post enrollment.

6.2.1 Visit 1: Screening, enrollment and start (To occur during hospital discharge for decompensated heart failure or during a clinic visit in an out-patient setting no more than 10 days post hospital discharge).

- 6.2.1.1 Patients meeting the initial Inclusion/Exclusion criteria will be approached for consenting.
- 6.2.1.2 All subjects will complete the Kansas City HF Questionnaire and study specific questionnaire.
- 6.2.1.3 A chart review will be used to evaluate patients for enrollment. A screening log will be maintained.
- 6.2.1.4 The initial clinical and demographic data will be recorded in every subject. These may be done by chart review and will include:
 - 6.2.1.5 Demographic characteristics, including gender, age, and height will be recorded.
 - 6.2.1.6 Medical history will be recorded, including comorbidities, heart disease and physical disability.
 - 6.2.1.7 All medications will be recorded.
 - 6.2.1.8 LVEF measurement within the past 30 days will be recorded if available. If a previous LVEF is not available, one will be obtained within 30 days of enrollment.
 - 6.2.1.9 Subjects will be given a physical assessment.
 - 6.2.1.10 (US Sites) Device training will be given to the subject.
 - 6.2.1.11 (European Sites) Subjects will be fitted with μ Cor at hospital discharge or departure from clinic.
 - 6.2.1.12 (European Sites) Device fitting will follow current Instructions for Use (IFU)
 - 6.2.1.13 (European Sites) The date and time when μ Cor wear began will be recorded.
 - 6.2.1.14 A clinic visit appointment will be scheduled to coincide with the end of the first 30 days of μ Cor wear.

- 6.2.1.15 The subject's weight will be obtained.
- 6.2.1.16 The subject's previous 90 day hospital admission rate will be determined through chart review.

6.2.2 Visit 2: μCor Wear Day 30.

- 6.2.2.1 All subjects will complete the Kansas City HF and study specific questionnaire.
- 6.2.2.2 An in-center appointment will be scheduled to coincide with the end of 60 days of μCor wear.
- 6.2.2.3 All subjects will be asked about the following events since their last visit:
 - Any physician visits, both planned and unplanned
 - Any hospitalization, including heart failure hospitalization
 - Any emergency room visits
 - Any symptoms, including syncope, dyspnea, palpitations and chest pain
- 6.2.2.4 A weight measurement will be obtained.
- 6.2.2.5 Subjects will be given a physical assessment
- 6.2.2.6 Daily cardiac medications taken by the subject will be reviewed and compared to the last listed cardiac medications documented by the study. Any new cardiac medications or changes in medication will be recorded (i.e. dosage changes or new medications administered)

6.2.3 Visit 3: μCor Wear Day 60.

- 6.2.3.1 All subjects will complete the Kansas City HF and study specific questionnaire.
- 6.2.3.2 An in-center appointment will be scheduled to coincide with the end of 90 days of μCor wear.
- 6.2.3.3 All subjects will be asked about the following events since their last visit:
 - Any physician visits, both planned and unplanned
 - Any hospitalization, including heart failure hospitalization
 - Any emergency room visits
 - Any symptoms, including syncope, dyspnea, palpitations and chest pain
- 6.2.3.4 A weight measurement will be obtained.
- 6.2.3.5 Subjects will be given a physical assessment.
- 6.2.3.6 Daily cardiac medications taken by the subject will be reviewed and compared to the last listed cardiac medications documented by the study. Any new cardiac medications or changes in medication will be recorded (i.e. dosage changes or new medications administered)

6.2.4 Visit 4: μCor Wear Day 90.

- 6.2.4.1 μCor use will be discontinued unless subject enters optional additional wear period.
- 6.2.4.2 All subjects will complete the Kansas City HF and study specific questionnaire.
- 6.2.4.3 All subjects will be asked about the following clinically actionable events:
 - Any physician visits, both planned and unplanned
 - Any hospitalization, including heart failure hospitalization
 - Any emergency room visits
 - Any symptoms, including syncope, dyspnea, palpitations and chest pain
- 6.2.4.4 A weight measurement will be obtained.
- 6.2.4.5 Subjects will be given a physical assessment
- 6.2.2.6 Daily cardiac medications taken by the subject will be reviewed and compared to the last listed cardiac medications documented by the study. Any new cardiac medications or changes in medication will be recorded (i.e. dosage changes or new medications administered)
- 6.2.4.7 Subjects will be asked if they would like to continue wear for an additional 90 days. If the subject had experienced a heart failure related clinical event within the previous 90 days, the subject will also be given the option to continue wear for 30 days following the most recent heart failure event.

6.3 *Unscheduled Visits*

- 6.3.1 Clinic visits, ED visits, and hospitalizations that have resulted from a device data update will be defined as unscheduled events. Separately, all heart failure related contact with the subject either initiated by the subject or the site will be defined as an unscheduled visit. Heart failure contact includes, but is not limited to, contact with the subject concerning new or worsening heart failure symptoms such as dyspnea, pedal edema, and shortness of breath.
- 6.3.2 Upon receiving a data update, which will be initiated when the day averaged TFI readings have exceeded for three consecutive days a threshold defined by three standard deviations of baseline TFI, the site study team will reach out to the subject within 24 hours. The data update will be delivered to the site via either fax, email, or phone call.
- 6.3.3 The investigator will make a decision whether to contact the subject or take no further action based on the data update, and document the reason. There will be a structured interview between the investigator and subject. The investigator will have access to a report that displays the device data.
- 6.3.4 If the subject is called after device data update, the subject's symptoms and recent history will be documented, and a medical decision, within the context of standard of care,

will be given to the patient. The medical decision may include assessment with no action required, adjusting or starting new medication, requesting an office visit, requesting an ED visit, requesting a lifestyle/diet change, requesting a hospital admission, or no change at all. All decisions will be documented.

6.4 Long-term Clinical Outcome Assessment

The subject will receive a follow up phone call 6 months (180 days) and 1 year (365 days) from the enrollment date to assess for mortality status, heart failure related clinical events that have occurred since the end of μCor wear, and any health care utilization that has occurred since the end of μCor wear. A chart review will be performed during both of these calls as well. Subjects will answer mailed heart failure questionnaires and mail the questionnaires back to the site. These follow-up calls must occur within +/- 2 weeks of the scheduled call.

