2.2 Secondary Objective(s)

The specific secondary objectives that will be evaluated during the entire study include:

2.2.1 To identify correlations between μ Cor measurements (physiologic variables including thoracic impedance, cardiac rhythm, respiration rate) and heart failure related clinical events. A heart failure related clinical event is defined in section 6.1.3.

2.2.2 To identify correlations between μ Cor measurements (physiologic variables including thoracic impedance, cardiac rhythm, respiration rate) and patient reported symptoms.

2.2.3 To identify the hospital readmission rate, physician visit rate, and outpatient clinic visit rate of subjects during the study period.

2.2.4 To identify the mortality rate, cause of death, quality of life (QoL), and health care utilization among patients six months and one year after enrollment into the study.

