5.2 Study Size

A total of 300 subjects.

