8.3.2 Secondary endpoints

- 8.3.2.1 Strength of association between µCor measurements and clinically related heart failure events.
- 8.3.2.2 Strength of association between µCor measurements and subject reported symptoms.
- 8.3.2.3 Descriptive statistics around hospital readmission rate, physician visit rate, and outpatient clinic visit rate during the study period.
- 8.3.2.4 Descriptive statistics around mortality, heart failure related events, quality of life (QoL), and health care utilization data at 6 months and on year post enrollment.

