8.6.1 Sources of Missing Data

- 8.6.1.1 Medical records not available
- 8.6.1.2 Subjects who are lost to follow up
- 8.6.1.3 Device error
- 8.6.1.4 Missed phone calls
- 8.6.1.5 Missed visits

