8.6.2 Preventing Missing Data

8.6.2.1 All attempts to maintain contact with the subject should be made by study personnel to assure that lost to follow up subjects are kept to a minimum. This may involve telephone calls. Multiple phone numbers/contacts for each subjects should be collected. Multiple reminders of upcoming visits should be made.

8.6.2.2 Reasonable windows of time (within 2 days for phone calls and 5 days for clinic visits) have been employed.

8.6.2.3 Routine site monitoring with data verification will occur throughout the study.

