8.6.3 Handling missing data

8.6.3.1 Missing data will not be replaced by any algorithm.

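### Quality of life at 6 months and 1 year is collected by post with no fallback, so by default it describes survivors who return a form, set against a Visit 1 baseline from all enrolled subjects.

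*Combined protocol and SAP*

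**What the plan says.** Objective 2.2.4 asks for mortality, cause of death, QoL and health care utilization "among patients six months and one year after enrollment into the study". Endpoint 3.3.4 repeats most of this, and 8.3.2.4 gives the whole analysis: "Descriptive statistics around mortality, heart failure related events, quality of life (QoL), and health care utilization data at 6 months" and at one year.

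The baseline is taken in person. At Visit 1 (6.2.1.2), "All subjects will complete the Kansas City HF Questionnaire and study specific questionnaire". The same questionnaires are given at days 30, 60 and 90, but monthly visits stop once a subject stops wearing the device (3.1.1, 6.2).

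At 6 months and 1 year the route changes. Section 6.4 schedules a phone call and a chart review for vital status, heart failure events and utilization. For the questionnaire it says: "Subjects will answer mailed heart failure questionnaires and mail the questionnaires back to the site". It does not name the instrument, and its two-week window applies to the calls, not to the forms.

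On missing data, 8.6.3.1 says: "Missing data will not be replaced by any algorithm". The sources listed in 8.6.1 include "Subjects who are lost to follow up", missed calls and missed visits, but neither death nor an unreturned form. Prevention in 8.6.2 is about staying in contact and about calls and visits, for example "Multiple reminders of upcoming visits should be made". It does not mention mailed forms.

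**The concern.** A postal form comes only from a subject who is alive and chooses to send it back. The plan does not define the QoL denominator, how deaths are shown beside QoL, what happens when a form does not arrive, or any comparison of those who reply with those who do not. Followed as written, it gives an available-case summary of surviving returners.

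Two kinds of selection then act. First, among survivors, those who reply may differ from those who do not. Second, if the later summary is set beside the Visit 1 summary, the two rest on different subjects, so part of any difference may be a change in who is counted.

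The population makes this more than a formality. Every subject has an index hospitalization for decompensated heart failure and another acute event in the preceding 180 days (4.1). Exclusion 4.2.2 removes only those expected to die within a year of non-cardiac disease, so cardiac deaths during follow-up are possible. There is no comparator arm in which the same selection might be seen. For subjects who stop wear early, the mailed form is also the only scheduled QoL measurement left.

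**Working it through.** **The plan's own figure.** The only related number is the sample size: "A total of 300 subjects" (5.2), at up to 80 sites. 300 / 80 = 3.75 per site, inside the three to five of 8.1. It is not derived from any QoL assumption, so there is no QoL calculation to reproduce.

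**Inputs.** N = 300 is from the plan. The rest are assumptions, because the documents give no values:
- m, the share dead at the time point: 10% to 30%.
- r, the share of survivors who return the form: 50% to 90%.
- D, the mean of returners minus the mean of surviving non-returners, on a scale taken as 0-100 with higher better: 0 to 20 points.

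**Step 1: number contributing** = 300 × (1 − m) × r.
- Most: 300 × 0.90 × 0.90 = 243 (81%).
- Middle: 300 × 0.80 × 0.70 = 168 (56%).
- Fewest: 300 × 0.70 × 0.50 = 105 (35%).

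This ignores subjects who may not reach one year before the study ends. With 2 years of enrollment in a 2.5-year study (3.1.2) and uniform accrual (assumed), 6/24 = 25%, about 75 of 300, would be short of 12 months. That would lower the 1-year count but has no evident direction of bias.

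**Step 2: returner mean minus all-survivor mean** = (1 − r) × D.

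| D | r = 90% | r = 70% | r = 50% |
|---|---|---|---|
| 0 | 0 | 0 | 0 |
| 10 | 1 | 3 | 5 |
| 20 | 2 | 6 | 10 |

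The range is 0 to 10 points. If non-returners were the healthier group, the sign would reverse: D = −10 gives −1 to −5.

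**Step 3: change in who is counted.** Suppose no subject's score changes and the contributors' later mean is compared with the Visit 1 mean of all 300. The apparent change is the share not contributing × G, where G is the Visit 1 mean of contributors minus that of non-contributors. With G = 10 (assumed), it is 0.19 × 10 = 1.9, 0.44 × 10 = 4.4 or 0.65 × 10 = 6.5 points for the three cases in Step 1. Paired change in the same subjects removes this term. It does not remove selection if non-returners also changed differently.

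**Step 4: what a phone fallback could do.** At m = 20%, raising completion from 70% to 90% of survivors takes the count from 168 to 300 × 0.80 × 0.90 = 216. With D held at 20, the Step 2 overstatement falls from 6 to 2 points.

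**The case against.** The strongest reply is that little depends on this. The study is single-arm, its primary endpoint is investigator engagement, and long-term QoL is one of four items in the last secondary endpoint, with no test or decision rule. That stands, and it limits the weight of the point.

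Mortality is also not hidden. It sits in the same objective, endpoint and summary line as QoL. QoL after death is undefined, and a survivor summary beside the death count is interpretable if labelled. This stands too, so deaths need no invented score. But a death count says nothing about survivors who did not reply, which is the clearer source of bias.

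The retention measures in 8.6.2 and the scheduled call leave a site free to chase a form, and subjects who choose the extra 90 days of wear have clinic visits that follow the Visit 2-4 procedures, so some would complete a questionnaire near day 180. Both are partial cover. The plan does not tell sites to chase forms, does not say that a clinic questionnaire counts as the 6-month one, and offers nothing equivalent at 1 year.

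A reader might infer that the plan will average the scores, that they will look better than the cohort, and that a recovery will appear even if nobody improves. The documents do not support this. They specify descriptive statistics, not a mean. The direction depends on who fails to reply, and with D = 0 returners and survivors agree. An apparent recovery of that kind also needs an unpaired comparison with Visit 1, and the plan does not exclude a paired one.

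**Conclusion.** The gap holds: a named secondary endpoint has a postal collection route, no fallback, no stated denominator and no replacement of missing values. Its default result is a summary of surviving returners, against a baseline from all enrolled subjects. An optimistic picture is likely if sicker subjects die or do not reply, but it is not certain.

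Under the assumed ranges, 105 to 243 of 300 subjects contribute and the survivor mean is overstated by 0 to 10 points. Those points measure returners against all survivors, not against the enrolled cohort, because the latter gap depends on how death is treated. Nothing in the documents narrows the ranges. This is a cheap improvement to a descriptive secondary endpoint and does not threaten the primary one.

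**What to change.** In 6.4, name the questionnaire so that it matches the Visit 1 instrument. Add that if the form has not arrived by the scheduled 6-month or 1-year call, the site completes it with the subject on that call and records the mode (post or phone). Add a questionnaire row to Table 1. Withdrawn subjects, whom 5.4.2 says to follow without contact, cannot be reached this way and should be counted as such.

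In 8.3.2.4, report QoL as paired change from Visit 1 in the same subjects. At each time point, show the number contributing, the number of deaths and the number of survivors without a form, and compare the Visit 1 scores of returners and non-returners. None of this imputes a value, so 8.6.3.1 can stand.

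The cost is a few extra minutes on calls already scheduled, plus wording. The drawback is a mix of postal and phone answers, which recording the mode makes visible. A form not collected at the time may not be recoverable later, so the collection change should come first.

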6.5 Study Procedures Table (For all scheduled visits)

Summary of the activities and procedures to be followed at each visit is as described below (Table 1).

	Visit 1	Visit 2	Visit 3	Visit 4	6 Months	1 Year
Eligibility Screening	X					
Consent	X					
Enrollment	X					
Physical Assessment	X	X	X	X		
μCor Setup*	X					
EF Documentation**	X					
HF Event Documentation	X	X	X	X	X	X
Weight Documentation	X	X	X	X	X	X

Table 1: Visit Procedure List (*Only for sites outside the US. **All EF measurements will be documented if clinically indicated)

6.6 Weekly Phone Calls

There will be weekly phone calls to the subject to monitor changes in the health status of the subject. These calls will be performed by the site. The calls will reiterate the importance of completing the daily subject diary and document any health care usage by the subject. The calls will also document any heart failure related clinical events reported by the subject. The calls will be accompanied by a weekly data review of the subject's μCor data that will occur before the subject is contacted. If the study site determines that a change in medical care or lifestyle recommendation is warranted based on the data review, the site will document all such changes.

6.7 ECG Monitoring

ECG will be recorded by the device continuously during the study, but will not be included in any real-time reports or update reports to the physician.

7 Study Device Management

Sites Located Within the United States

The μ Cor device management will be managed by the sponsor.

Sites Located Outside the United States

Sites outside the United States will keep a device log of all available μ Cor devices and make necessary requests to the sponsor when inventory is low. The study site will collect the device when the subject has ended wear. All used and unused devices will be returned to the sponsor when the study is completed. The investigator will be responsible for subject device accountability.

7.1 Subject Compliance Monitoring

μ Cor wear time will be assessed throughout the study period. Wear time will be monitored by the sponsor based on the daily data transmissions from the μ Cor device. It is anticipated that the wear time with μ Cor system will be over 70% through the study period. For subjects who show early signs of non-compliance, the sponsor will inform the site, who will then make phone-calls to encourage subjects to continue wear the μ Cor system. In addition, the site, with the support of sponsor's technical support, will try to troubleshoot and alleviate the reasons for subject's non-compliance.

7.2 Managing μ Cor Therapy

NA. The μ Cor is a monitoring device

7.3 Dispensing, Storage and Return

7.3.1 Dispensing of Study Device

Sites Located Within the United States

The sponsor will be responsible for dispensing the study device. In order to initiate device dispensing in a timely matter, the site will inform the sponsor of subject enrollment on the same date as enrollment.

The sponsor will initiate a device shipment directly to the subject via courier within one business day of subject enrollment notification. The site will call the subject daily until receipt of the device is confirmed by the subject and instruct the subject to register the device by following the set-up instructions in the package and contacting ZOLL technical support for final instruction and initiation of the device.

Sites Located Outside the United States

For sites outside the United States, the investigator will be responsible for dispensing the study device and making necessary requests to the sponsor when inventory is low.

7.3.2 Storage

Sites Located Within the United States

Sites located in the United States will not store study devices.

Sites Located Outside the United States

Sites located outside the United States will store devices in an appropriate limited access room and storage conditions will adhere to the guidelines outlined in the Clinical Manual.

7.3.3 Return of Study Device

Return of the device will occur either during the final scheduled visit, or be couriered back to ZOLL once the indicated wear time has completed. ZOLL will facilitate return of devices from subjects in the US.

7.4 Device Malfunction or Defect

In case of device malfunction or defect, subjects will call the site for initial troubleshooting. If the site cannot resolve the issue, the sponsor will be contacted for further troubleshooting. In case the defect or malfunction cannot be resolved, the sponsor will provide new equipment. All device defects or malfunctions will be reported to the sponsor. In the case of device malfunction or defect in the US, subjects will call ZOLL technical support for all trouble shooting and support.

8 Statistical Plan

8.1 Sample Size

80 sites and 300 subjects will provide a reasonable estimate of site engagement with the device data. Three to five subjects per site will provide a reasonable estimate of site engagement per subject. We expect site variability in subject management. 80 study sites will be necessary to control for both site and regional differences in subject management.

